#### **5.3.3.4. Length Of ICU 'Care Free' Stay/Hospital Stay**

Patient stay in the ICU and Hospital setting is also recorded daily in the Patient Status record. The Number of ICU care free days and the Number of days in hospital is derived from this information using defined rules and algorithms specified in Section 5.9.4, Appendix 4. Again patients who die during this period will be assigned a value of zero.

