### ***5.3.3.3. Days Free Of Organ Failure, Renal Support, Vasoactive Support Evaluations***

Patient assessment of Organ failure, Renal support and Vasoactive support is also recorded daily in the Patient Status record.

The Number of days free of Organ failure, Renal support and Vasoactive support is derived from this information using defined rules and algorithms specified in Section 5.9.4. Patients who die during this period will be assigned a value of zero.

A patient will be defined as being free of organ failure when the SOFA score is zero. However, as organ failure is only assessed at Day 21 and Day 28 after Day 14 a scoring scheme will be used to derive the total number of days.

This is:

If Day 21 and Day 28 are both zero then 50% of the days between Day 14 and Day 21 and 100% of the days between Day 21 and Day 28 will be assumed to be zero.

If Day 21 is non-zero and Day 28 is zero then 100% of the days between Day 14 and Day 21 will be assumed to be non-zero and 50% of the days between Day 21 and Day 28 will be assumed to be zero.

Finally if Day 21 is zero and Day 28 is non-zero then 50% of the days between Day 14 and Day 21 will be assumed to be zero and 100% of the days between Day 21 and Day 28 will be assumed to be non-zero (also see Section 5.9.4.2, Appendix 4).

The need for Renal support or for Vasoactive support is defined in the protocol.

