### **5.5 Pharmacoeconomic Evaluations**

The total cost of treatment and care whilst patients are confined in the ICU (up to Day 28) will be derived from key individual patient efficacy measures and assigned unit costs for each measure.

UK Unit costs are considered representative and are given in Table 4.

Specific efficacy measures used are: Days free of organ failure, Days free of renal support, Days free of vasoactive support, Days free of mechanical ventilation, Number of ICU-free days, Number of days spent in hospital.

Individual patient need for these services will be determined in terms of days of use (subtracted from 28 for 'days free' or actual for 'days spent') and these will be multiplied by the daily costs to derive a total cost burden for each service and overall services.

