### ***5.9.6 Strategy For Missing Data***

No biases resulting from missing data are anticipated and, as a consequence No imputation of any missing values at any of the assessments performed is planned.

However, to allow for patient attrition or any changes to the scheduled patient assessments as a consequence of the treatment response a 'Last observation performed' assessment will be derived for specific Short term efficacy (Ventilation assessment, System Organ Failure (SOFA), Cardiovascular, Pulmonary and Renal function), Pharmacodynamic (IFN $\beta$  ADA & Nab, MxA, CD73, PIM) and Safety variables (Vital signs and Laboratory assessments). This approach will use the last available non-missing post baseline value.

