#### ***6.2.4.2 Days Free Of Mechanical Ventilation Analysis***

The actual Total number of days free of mechanical ventilation (not the derived VFD scores which require additional conditions of UAB to be met) will be numerically summarised (excluding means and standard deviations) according to Treatment group (FP-1201-lyo/Placebo), Severity of ARDS (Moderate/Severe) and Overall. Separate supporting summaries by Country will be included.

These endpoints will be analysed using the same methods as for the primary efficacy variable, VFDsurv, using the Van Elteren hypothesis test as the distribution is likely to be non-normal and negatively skewed by patients who are assigned scores of zero (0) in the event of death.

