#### ***6.2.4.4 Length Of ICU 'Care Free' Stay/Hospital Stay Analysis***

Totals derived will be numerically summarised and analysed as described in Section 6.2.4.2 above.

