### **7.2.3.2 Primary Efficacy Analysis - Ventilation Free Survival (VFDsurv)**

VFDsurv scores derived will be numerically summarised (excluding means and standard deviations) according to Treatment group (FP-1201-lyo/Placebo), Severity of ARDS (Moderate/Severe) and Overall. Statistical significance overall (Van Elteren p-values) will be displayed with the numerical summaries. Both FAS and PPS group analyses will be given (Table 14.2.2.1.1). Table 14.2.2.1.1 will also display secondary efficacy variables in the same manner, including Ventilation Free Days (VFD), Days Free of Organ Failure, Days Free of Renal Support, Days Free of Vasoactive Support, Days Free of Mechanical Ventilation, Number Of ICU Care Free Days, Number of ICU days and Number of Days In Hospital.

A frequency distribution (Table 14.2.2.2), together with Box and Whisker plots (Figures 14.2.1) of the VFDsurv scores will be presented by Treatment group and by Severity of ARDS for both FAS and PPS populations.

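### As written in the SAP body, deaths score zero days in hospital and so rank as the shortest stay, and each death is costed as 28 days of five services, including days after death

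*SAP*

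**What the plan says.** SAP 5.3.3.4 introduces two variables together, ICU care-free days and days in hospital, and then states: "Again patients who die during this period will be assigned a value of zero". It makes no exception for hospital days. SAP 6.2.4.4 gives the analysis of both: "Totals derived will be numerically summarised and analysed as described in Section 6.2.4.2 above". SAP 6.2.4.2 in turn says: "These endpoints will be analysed using the same methods as for the primary efficacy variable, VFDsurv, using the Van Elteren hypothesis test". SAP 7.2.3.2 puts the results in the table that carries the van Elteren p-values, and lists "Number Of ICU Care Free Days, Number of ICU days and Number of Days In Hospital" there. The SAP body states no death rule for the second of these, the number of ICU days.

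Protocol 8.5.2.2 sets zero at death for ICU-free days only. It has no such rule for days in hospital.

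SAP 5.3.3.2 and 5.3.3.3 also give deaths zero for days free of ventilation, organ failure, renal support and vasoactive support. SAP 5.5 then converts the same variables into days of service use: "subtracted from 28 for 'days free' or actual for 'days spent". Its stated aim is narrower: "The total cost of treatment and care whilst patients are confined in the ICU (up to Day 28) will be derived" from patient measures and unit costs. SAP 6.2.6 makes the log of total cost the response in an ANOVA.

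**The concern.** Zero at death makes sense for a free-days endpoint, where low is bad. Days in hospital runs the other way: low means a short stay. Every treated patient starts in the ICU, so a survivor has at least one hospital day and deaths alone hold the lowest rank. A drug that saves lives would then tend to look as if it prolongs hospital stay.

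The costing reuses the same zeros for a purpose they were not built for. As an efficacy score, zero is a penalty. Subtracted from 28, it becomes a claim that the patient used the service on all 28 days, including days after death.

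At stake are the reading of one named secondary endpoint and the input to the economic analysis.

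**Working it through.** **The plan's own figure.** Protocol 8.10 gives two-sided 0.05, 90% power, mortality 30% v 15%, 20% of control patients alive with zero ventilator-free days, and 272 evaluable patients. The Table 6 row for 3.0 days puts the drug arm at 14% alive with zero. Spreading the remaining 50% (control) and 71% (drug) evenly over 1–28 days gives P(drug better) = 0.611 and a Mann–Whitney total of 274. Simulated power at 272 is 90.0%. The figure is reproduced, and the same rank-test approach is used below.

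**Hospital days, direction.** Score deaths 0 and survivors at least 1, and assume the same survivor stays in both arms. With mortality 0.15 (drug) and 0.30 (placebo), and ties counted as one half:

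P(longer on drug) = 0.85 × 0.30 + 0.5 × 0.85 × 0.70 + 0.5 × 0.15 × 0.30 = 0.255 + 0.2975 + 0.0225 = 0.575.

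This equals 0.5 + (0.30 − 0.15)/2, so the shape of the shared stay distribution does not matter. At 30% v 18% it is 0.56. If deaths are ranked as the longest stay, it is 0.425.

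**Hospital days, how often significant.** The documents give no stay distribution, so one is assumed: a share of survivors is still in hospital on Day 28, and the rest leave uniformly over Days 8–27. There were 20,000 simulated trials with 136 per arm. The van Elteren row uses 16 equal strata (8 countries × 2 severities, no stratum effect). Entries are the percentage of trials significant for a longer stay on drug, with identical survivor stays.

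| Share still in hospital at Day 28 | 10% | 40% | 70% |
|---|---|---|---|
| Rank test, 15% v 30% | 58.2 | 59.5 | 65.7 |
| Van Elteren, 15% v 30% | 56.3 | 57.9 | 64.8 |
| Rank test, 18% v 30% | 40.5 | 41.4 | 46.9 |

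If drug survivors leave 1–2 days earlier, the rate at 15% v 30% runs from 0% to 62%, depending on who leaves earlier and on the share staying to Day 28.

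**Cost.** Each death is charged 28 − 0 = 28 days for each of five services (ICU, ventilation, renal, vasoactive, organ failure), which is 5 × 28 = 140 service-days. A patient who dies on Day 5 can have used at most 5 × 5 = 25. Deaths contribute 0.30 × 140 = 42 service-days per placebo patient and 0.15 × 140 = 21 per drug patient.

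Let d be the mean day of death, assumed equal in both arms. The post-death part of the placebo-minus-drug excess, per patient and per service, is (0.30 − 0.15) × (28 − d):

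- d = 5: 0.15 × 23 = 3.45 days
- d = 10: 0.15 × 18 = 2.70 days
- d = 20: 0.15 × 8 = 1.20 days

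Days before death on which a service was not used are also charged. They add 0.30 × u(placebo) − 0.15 × u(drug), where u is the mean number of such days among deaths. The documents do not give u.

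**The case against.** The strongest objection is that the operative rules are not visible. SAP 5.3.3.4 and 5.9.4 send the derivations to Appendix 4, whose text was not available for this review; that is not a gap in the plan. Parts of the body also point the other way: SAP 5.3.1 derives totals of days spent in ICU and hospital, and SAP 5.5 uses actual values for days spent, so the zero may not reach the hospital item in the costing. This limits certainty, but the zero rule is stated in the body itself. If Appendix 4 differs, the SAP contradicts itself and still needs an edit. The five-service charge does not depend on how hospital days are costed.

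A second objection is low consequence. That stands. Hospital days are outside the hierarchy in SAP 6.1.3, costs are deferred to the Day 180 and/or Day 360 reports, and mortality is reported by arm, so a reader could see why stays differ.

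A third is that ranking deaths worst only reverses the sign. This also stands in part. With identical stays, mortality alone would favour the drug in 58–66% of trials if deaths rank worst, and in 14–50% if hospital-free days are tested. At equal mortality, a 2-day shorter stay is detected in about 19–20% of trials under any of the three scorings (one assumed distribution). The gain is that the result points the right way and is labelled as a composite, not that it isolates length of stay.

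Two stronger readings are tempting. A reader might take 58–66% as a property of this trial; it rests on assumed stays. A reader might also infer that the costing must favour the drug. The documents do not support that: the net excess depends on unused days before death, unit costs are still to be confirmed, and the planned analysis is on log cost.

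**Conclusion.** The concern holds for the SAP body as written. Deaths are scored as the shortest hospital stay and tested that way, and five services are costed for days after death, contrary to the stated aim of SAP 5.5.

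For hospital days, the firm result is 0.575 in favour of a longer stay on drug at the design mortality, given equal survivor stays. The 58–66% significance rate adds the assumed stay distributions. For cost, the firm result is the 28-day charge per service per death. The 3.45, 2.7 or 1.2 days rest on the design mortality and an assumed mean day of death common to both arms, and cover only the post-death part. The net effect on the log-cost ANOVA cannot be determined from the documents.

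The primary endpoint, the mortality tests, the hierarchy and the sample size are untouched. This should be fixed before unblinding, but it does not threaten the trial's main conclusion.

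**What to change.** Before unblinding, reconcile SAP 5.3.3.4 and 5.5 with Appendix 4, and make these changes.

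- **Hospital-stay test.** Do not score deaths zero on days in hospital. Either rank deaths worst, or test hospital-free days with deaths at zero, the form Protocol 8.5.2.2 uses for ICU-free days. Choose one, label it a composite with death, and report actual days to death or discharge descriptively.
- **Number of ICU days.** State a matching death rule.
- **Costing.** Cost the recorded days alive and on each service, and actual hospital days, up to death or Day 28. For transferred patients, use the recorded totals and death date (SAP 5.3.3.7).
- **Organ-failure days in the costing.** Use the daily SOFA scores to Day 14 and add an explicit rule for deaths on Days 15–27. The existing interpolation ("If Day 21 and Day 28 are both zero then 50% of the days between Day 14 and Day 21" and so on) needs a Day 28 score, which these patients lack. SAP 5.9.6 is not a precedent: it plans no imputation, and its derived last observation is a single summary value ("This approach will use the last available non-missing post baseline value"), not a day-by-day carry-forward.
- **Free-days efficacy endpoints.** Zero at death may stay for the others. For organ failure-free days, SAP 5.3.3.3 must be reconciled with Protocol 8.5.2.2, which counts days alive and free of organ failure and sets no zero at death.

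The cost is wording in the SAP, matching rules in Appendix 4, and derivation code. Hospital, ICU, ventilation, renal and vasoactive days need no new data, because status and date of death are already recorded. Organ-failure days need one stated rule, because SOFA is not scheduled daily after Day 14.

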#### **5.3.3.5 Sequential Organ Failure Assessment (SOFA)**

Organ failure status is assessed using the SOFA score. This assesses six organ systems and the score ranges from 0-24 with a score of zero indicating no organ failure (see Protocol for the scoring mechanism).

The scores are based on the worst daily values recorded for: Hypotension/Use of vasopressors (Cardiovascular score), PaO2/FiO2 (Respiratory score), Platelets (Coagulation score), Bilirubin (Hepatic score), Creatinine (Renal score) and Glasgow Coma Scale (GCS) (CNS score).

The SOFA score is assessed pre-dose on Day 1, then daily up to Day 14 and then at Day 21 and Day 28 In or Out of the ICU or at withdrawal (Early Termination).

The Last observation performed whether at Day 28 or earlier will be derived.

The change from baseline (Day 1 Pre-dose) will be calculated.

The values for each contributing variable in the scoring mechanism are recorded by the site staff in Patient Status record of the EDC system and the total scores are derived programmatically according to the algorithm specified in the protocol.

#### **5.3.3.6. Individual Organ Assessments**

A number of separate assessments are performed to assess the functioning of individual body organs including: Cardiovascular, Pulmonary and Renal.

##### **5.3.3.6.1 Cardiovascular Function**

The need for Vasoactive support is recorded daily in the Patient Status (Days 1 (Pre-dose) then daily on Days 2 - 28 (Day 28 In or Out of ICU) at the Medications update and specific details are recorded in the Concomitant infusion vasoactive medications record.

The Last observation performed whether at Day 28 or earlier will be derived.

The Number of days free of Vasoactive support is derived from this information using defined rules and algorithms specified in Section 5.9.4, Appendix 4.

### 5.3.3.6.2 Pulmonary Function

Ventilation assessments are recorded daily (Days 1 (Pre-dose) then daily on Days 2 - 28 (Day 28 In or Out of ICU).

Gas exchange measurements are performed. Measures include: Fraction inspired oxygen (FiO2), Partial pressure arterial oxygen (PaO2), PaO2/FiO2 ratio, PEEP together with a Baro-trauma classification (Yes/No). The PaO2/FiO2 ratio change from baseline will be used to assess pulmonary function.

The Last observation performed whether at Day 28 or earlier will be derived.

The change from baseline (Day 1 Pre-dose) will be calculated. However, Fraction inspired oxygen (FiO2), Partial pressure arterial oxygen (PaO2), PaO2/FiO2 ratio and PEEP may be measured at Day 1 dosing and, in this case, these values will be utilised for the change from baseline calculations.

Additional measurements of Peak inspiratory pressure, Plateau pressure, Mean airway pressure, Respiratory rate and Tidal volume are collected at Screening and Day 1 (Pre-dose) only.

At Day 1 Pre-dose and also at Day 28 (In or Out of ICU or earlier in the event of Early Termination) the severity status of ARDS will be classified as Mild (except Pre-dose/Day 1 dosing), Moderate, Severe or Death (Table 3) and numerically rated from 1-4 respectively.

Improvement is defined as a decrease in the severity score at the Last observation performed (Day 28 or earlier if withdrawn), No change is a zero change score and Worsening an increase in the severity score.

Both the Severity status and Change score (from Investigator CRF Day 1 dosing) classifications will be categorically summarised, and post Day 1 classifications will be calculated as follows:

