**Table 1 The Berlin ARDS Definition**

Characteristic	Mild ARDS	Moderate ARDS	Severe ARDS
Timing	Acute onset within 1 week of a known clinical insult or new or worsening respiratory symptoms		
Hypoxaemia	PaO 2 /FiO 2 >200–≤300 mmHg with PEEP or CPAP ≥5 cmH 2 O	PaO 2 /FiO 2 >100– ≤200 mmHg with PEEP ≥5 cmH 2 O	PaO 2 /FiO 2 ≤100 mmHg with PEEP ≥5 cmH 2 O
Origin of oedema	Respiratory failure associated with known ARDS risk factors and not fully explained by cardiac failure or fluid overload. An objective assessment of cardiac failure or fluid overload is needed if no ARDS risk factors are present		
Radiological abnormalities (chest X-ray or CT scan)	Bilateral opacities not fully explained by effusions, nodules, masses or lobar/lung collapse		

*Abbreviations: ARDS=acute respiratory distress syndrome; CPAP=continuous positive airway pressure; CT=computerised tomography; PaO2/FiO2=partial pressure of oxygen/fraction of inspired oxygen; PEEP=positive end expiratory pressure.*

The mortality rates in patients with ARDS range from approximately 20% to 40% across all severities, and can be even higher when associated with dysfunction in other organs. Although mortality from ARDS has decreased in the last decade due to improvements in supportive care and in the treatment of underlying conditions, it still remains at a high level.

ARDS is also costly in health economics terms. Patients with ARDS consume significantly more resources than matched patients without moderate or severe ARDS

because they require longer intensive care unit (ICU) and hospital stays. The quality of life (QoL) of these patients may also be significantly impacted, with 35% of patients with moderate or severe ARDS unable to return to work 24 months after hospital discharge.

There are currently no approved pharmacological therapies for ARDS. ARDS has no primary treatments proven to improve outcomes other than supportive care.

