#### **6.5 Exploratory Variables**

##### **6.5.1 Improvement in Gas Exchange**

The gas exchange ( $\text{PaO}_2/\text{FiO}_2$  ratio) of patients on mechanical ventilation will be evaluated. The  $\text{PaO}_2/\text{FiO}_2$  ratio will be used as an indicator of lung function.

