### 3.3 Weaning Procedures

Where there is an ICU weaning policy on ventilation this should be followed. In the absence of a unit policy the guidelines below should be followed.

- Patients should be assessed for the following weaning readiness criteria each day between 06:00 and 12:00. This assessment will NOT be performed within the first 24 hours after randomisation.
  - a)  $\text{PaO}_2/\text{FiO}_2 > 300$  after 1 hour with PEEP  $< 10$  and  $\text{FiO}_2 < 0.5$
  - b) Values of both PEEP and  $\text{FiO}_2 \leq$  values from previous day
  - c) The patient is not receiving neuromuscular blocking agents
  - d) The patient is exhibiting inspiratory efforts
  - e) Systolic arterial pressure  $\geq 90$  mmHg without vasopressor support ( $\leq 5$   $\mu\text{g}/\text{kg}/\text{min}$  dopamine or dobutamine will not be considered vasopressor support in this context)
- If criteria a–e are met, application of respiratory management as per protocol will be terminated and, in the treatment group, extra-corporeal carbon dioxide removal will be interrupted and vascular catheters removed. Clinicians will then be free to use any ventilation protocol they consider clinically appropriate.
- A spontaneous breathing trial (SBT) procedure and assessment for unassisted breathing will be performed. The SBT will take place over up to 120 minutes of spontaneous breathing with  $\text{FiO}_2 < 0.5$  using any of the following approaches:
  - a) Pressure support (PS)  $< 5$   $\text{cmH}_2\text{O}$ , PEEP  $< 5$   $\text{cmH}_2\text{O}$
  - b) Continuous positive airway pressure (CPAP)  $< 5$   $\text{cmH}_2\text{O}$
  - c) T-piece
  - d) Tracheotomy mask
- Criteria for reporting a SBT as “**successful**” are:
  - a)  $\text{SpO}_2 \geq 90\%$  and/or  $\text{PaO}_2 \geq 60$  mmHg
  - b) Respiratory rate  $\leq 35/\text{min}$
  - c)  $\text{pH} \geq 7.30$
  - d) No respiratory distress (defined as  $\geq 2$  of the following):

- Heart rate  $\geq 120\%$  of the rate at 06:00 ( $\leq 5$  min at  $\geq 120\%$  may be tolerated)
- Marked use of accessory muscles
- Abdominal paradox
- Diaphoresis
- Marked subjective dyspnoea

If any of criteria a–d are not met, the SBT will be reported as “**unsuccessful**” and previous ventilator settings will be initiated or PS  $\geq 10$  cmH2O with PEEP and FiO2 = previous settings. The patient should be reassessed for weaning the following day.

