**Table 3: ARDS Severity Classification Post Day 1**

ARDS Severity	Variable	Criteria
Mild -1	PaO 2 /FiO 2 Ratio	200 mmHg < PaO 2 /FIO 2 ≤ 300 mmHg
Moderate-2	PaO 2 /FiO 2 Ratio	100 mmHg < PaO 2 /FIO 2 ≤ 200 mmHg
Severe-3	PaO 2 /FiO 2 Ratio	PaO 2 /FIO 2 ≤ 100 mmHg
Death-4	(Patient Status)	Yes/No

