## **6. Statistical Methods**

### ***6.1 General Considerations***

All data derivations, manipulations and reporting procedures will use SAS v9.4 in a Windows 7 operating system environment.

For all evaluations, data will be described and analysed according to Treatment group (FP-1201-lyo/Placebo), Severity of ARDS (Moderate/Severe) and Country (1-8) and where appropriate Assessment period (Screening, Day 1 Pre-Dose, Short Term Follow Up (Day 1-28 ICU based), Long Term Follow Up (Day 90, Day 180) and Extended Follow Up (Day 360)) will be included. In addition, other endpoints summarising overall response are derived and analysed (e.g.: VFDsurv - the survival plus days free from mechanical ventilation composite).

All the data collected are to be summarised, and the descriptive statistics produced will account for the nature and distribution of the data collected. For continuous variables, data will be presented as number (n), mean, median, standard deviation, and range. For discrete variables data

will be presented as frequencies and proportions (as appropriate) and the denominator will be the number of patients available in the relevant population.

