##### **6.2.4.6.2 Pulmonary Function**

Ventilation assessments recorded daily (Day 1 (Pre-dose/Day 1 dosing) then daily on Days 2 - 28 (Day 28 In or Out of ICU) will be numerically summarised (with the derived Last observation performed) using the actual values and change from baseline values by Treatment group (FP-1201-lyo/Placebo), Severity of ARDS (Moderate/Severe) and Overall for each assessment time using the FAS population. Separate supporting summaries by Country will be included.

Each of the gas exchange variables measured will be reported but the PaO2/FiO2 ratio change from baseline will be used to assess pulmonary function.

In addition, an Analysis of Covariance (ANCOVA) model, similar to the Total SOFA scores in Section 6.2.4.5 will include the PaO2/FiO2 ratio change from baseline value as the response variable at the Last observation performed assessment time.

Homogeneity of treatment effect will be assessed as for the SOFA score.

The Severity status and Change score classifications derived over the period of confinement within the ICU will be categorically summarised according Treatment group (FP-1201-lyo/Placebo), Severity of ARDS (Moderate/Severe) and overall using the FAS population.

The derived overall Change score classification (Improved, No Change, Worsened) will be analysed using the Cochran-Mantel-Haenszel hypothesis test including Severity of ARDS and Country as stratification variables. Statistical significance (p-value) overall will be displayed with the categorical summaries. Summary counts will be presented by severity of ARDS (Moderate/Severe).

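### SAP Table 3 closes Mild at a PaO2/FiO2 ratio of 300 mmHg, so under the visible text a survivor whose last ratio is above 300 gets no severity class and no change score (exploratory endpoint)

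*SAP*

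**What the plan says.** SAP 5.3.3.6.2 (Pulmonary Function) states that severity status "will be classified as Mild (except Pre-dose/Day 1 dosing), Moderate, Severe or Death (Table 3"), with ratings from 1 for Mild to 4 for Death. Improvement is a lower rating at the last observation performed, no change is an equal rating, and worsening is a higher one. The section adds that "post Day 1 classifications will be calculated as follows", which points to Table 3, "ARDS Severity Classification Post Day 1":

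- Mild (1): ratio above 200 and up to 300 mmHg
- Moderate (2): above 100 and up to 200 mmHg
- Severe (3): 100 mmHg or below
- Death (4)

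No row lies above 300. The cap on Mild matches the protocol's Berlin definition (Table 1), ">200–≤300 mmHg with PEEP or CPAP". The protocol's own wording of the endpoint (3.2.4 and 8.8.2) also stops at mild.

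SAP 6.2.4.6.2 sets the test: "The derived overall Change score classification (Improved, No Change, Worsened) will be analysed using the Cochran-Mantel-Haenszel hypothesis test", stratified by severity and country. For discrete variables, SAP 6.1 says that "the denominator will be the number of patients available in the relevant population", and SAP 7.1 repeats this for categorical summaries. SAP 5.9.6 takes the last non-missing post-baseline value and plans no imputation.

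**The concern.** A definition made for diagnosing ARDS is being used as an outcome scale. For diagnosis, a ratio above 300 means that the patient does not qualify. As an outcome it is the best result on the scale, and it has no category. Mild is not allowed at pre-dose or Day 1 dosing, so anyone who finishes above 300 has improved from either possible baseline class.

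The documents foresee such ratios. The SOFA table (protocol Table 2) has respiration classes for 300 to 400 and for above 400. Freedom from organ failure requires a SOFA score of zero (protocol 6.1.2.1, SAP 5.3.3.3) and hence a ratio above 400, so a patient free of organ failure at the last assessment has no Table 3 class. The default weaning-readiness list in protocol Appendix 1 (3.3) begins with a ratio above 300. It applies only where the ICU has no policy of its own: "In the absence of a unit policy the guidelines below should be followed".

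At stake are the percentage Improved in each arm, the difference between arms, and the displayed CMH p-value for this one endpoint.

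**Working it through.** **Applying the rule.** Table 3 and the change-score definition, taken literally, give:

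| Last ratio (mmHg) or status | Class | From Moderate (2) | From Severe (3) |
|---|---|---|---|
| 100 | 3 | Worsened | No change |
| 101 or 200 | 2 | No change | Improved |
| 201 or 300 | 1 | Improved | Improved |
| 300.1, 301 or 400 | none | none | none |
| Death | 4 | Worsened | Worsened |

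The last-observation rule does not help, because a ratio of 301 is itself the last non-missing value.

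**Effect on the tables, if unscored patients stay in the denominator.** For each arm, let I be the proportion Improved when ratios above 300 are counted, and s the FAS proportion above 300. The table then shows I − s. The difference between arms (drug D minus placebo P) becomes

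(I_D − I_P) − (s_D − s_P).

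This identity needs no further assumption. The difference is understated if s is larger on drug, overstated if s is larger on placebo, and unchanged if the two are equal.

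**Illustration.** The plan has no figure of its own to reproduce here. From protocol 8.10: Day 28 mortality of 30% (placebo) and 15% (drug), and 272/2 = 136 patients per arm. Assumed: h, the share of survivors above 300, so that s = (1 − mortality) × h; and other survivors split 60/30/10 into Improved, No change and Worsened in both arms.

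Worked case, h = 20% placebo and 30% drug:
- Placebo: s = 0.70 × 0.20 = 14.0%. Improved at or below 300 = 0.60 × (70 − 14.0) = 33.6%. Counted total = 47.6%.
- Drug: s = 0.85 × 0.30 = 25.5%. Improved at or below 300 = 0.60 × (85 − 25.5) = 35.7%. Counted total = 61.2%.
- Difference counted = 61.2 − 47.6 = 13.6 points. As written = 35.7 − 33.6 = 2.1 points.
- Check: 13.6 − (25.5 − 14.0) = 2.1.

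The power columns compare patients above 300 counted as Improved with the same patients excluded. They come from simulating an unstratified CMH mean-score test with scores 1/0/−1 at two-sided 0.05. The SAP does not name the CMH statistic, so this is one plausible choice.

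| Mortality P/D | h P/D | Difference counted → as written (points) | Power counted vs excluded |
|---|---|---|---|
| 30/15% | 5/5% | 9.3 → 8.6 | 0.59 vs 0.58 |
| 30/15% | 20/20% | 10.2 → 7.2 | 0.63 vs 0.59 |
| 30/15% | 40/40% | 11.4 → 5.4 | 0.68 vs 0.59 |
| 30/15% | 20/30% | 13.6 → 2.1 | 0.77 vs 0.46 |
| 30/15% | 30/20% | 7.4 → 11.4 | 0.49 vs 0.71 |
| 30/30% | 20/20% | 0 → 0 | 0.05 vs 0.05 |
| 30/30% | 20/30% | 2.8 → −4.2 | 0.06 vs 0.07 |

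A check with 16 equal strata (2 severities × 8 countries) gave nearly the same power: 0.68 vs 0.58 for 40/40%, and 0.77 vs 0.45 for 20/30%, both at 30/15% mortality.

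At 30/15% mortality the table difference does not shift when h on drug is 0.70/0.85 = 0.82 times h on placebo, for example 24.7% against 30%.

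**The case against.** The strongest reply is that unseen text may settle the matter. Appendix 4 holds derivation rules for efficacy variables, and the shells for Tables 14.2.6.12 would show the actual categories. Neither was supplied, so their absence here is not a gap in the plan. This stands as a condition on the finding. It is weakened because 5.3.3.6.2 refers this classification to Table 3, while neighbouring sections refer their derivations to Appendix 4.

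Second, the denominator effect is an inference. Whether an unscored patient is available in the population is open. For laboratory data, SAP 7.3.5 adds a category for not done or missing; a similar row here would at least make the unscored patients visible. This also stands.

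Third, the blind review (SAP 6.1.5) examines the data and the structure of the table shells before unblinding, and might well reveal survivors with a ratio but no class. True, but it supplies no rule for scoring them.

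Fourth, few patients may be affected. Protocol 6.5.1 says that the ratio "of patients on mechanical ventilation will be evaluated", which may keep the share small. On the other side, SAP 5.3.3.6.2 classifies severity at Day 28 in or out of the ICU.

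Fifth, the intent is hardly in doubt. Agreed, but Table 3 as written contradicts that intent, and a programmer should not have to choose.

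A reader might infer that the gap biases the result against the drug. The documents do not support that: the direction depends on shares by arm that they do not give. Nor do they support a general claim of serious power loss. The larger power changes need high or unequal shares together with the assumed mortality gap, because death counts as Worsened. The endpoint has no power target in any case.

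**Conclusion.** The concern holds as a minor drafting error with a definite wrong result. Under the visible text, 300 mmHg is Improved and anything above it has no class or change score.

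If unscored patients remain in the denominator, the percentage Improved is too low in each arm by that arm's FAS share above 300, and the treatment difference moves by the difference between those shares. Removal from the CMH test is presumed, not stated.

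The size is unknown, and the power figures are illustrations only. With equal shares and 30/15% mortality, the power change runs from about 0.01 at 5% to about 0.09 at 40%, so it is not negligible at every equal share. With equal 30% mortality and shares of 20/30%, power barely changes (0.06 vs 0.07), although the tabulated difference still moves by 0.70 × (30 − 20) = 7.0 points.

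The protocol lists the endpoint as exploratory (3.2.4), and it is outside the testing hierarchy in SAP 6.1.3. The primary endpoint, mortality and the ANCOVA of the PaO2/FiO2 ratio are not touched. The conclusion is conditional on Appendix 4 and the table shells containing no rule.

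**What to change.** Before the Day 90 lock, make one of two changes to SAP Table 3:

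- change the Mild criterion to above 200 mmHg with no upper bound, and relabel it 'Mild or better' (ratings stay 1 to 4); or
- add a row 'No ARDS', rated 0, for ratios above 300 mmHg.

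Both give the same Improved, No change and Worsened results, because every baseline score is 2 or 3. The first is the smaller change.

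Add one sentence to 5.3.3.6.2 saying that a last observation above 300 mmHg counts as Improvement and is included in the CMH test. Keep the last-observation rule, and record that this clarifies protocol 3.2.4 and 8.8.2. If Appendix 4 already contains such a rule, cross-refer to it from Table 3 instead.

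The cost is one criterion or row and one sentence, with no new data. A reader might infer from protocol 9.7 that an amendment is needed. A SAP change should suffice, since protocol 8.8.2 leaves the details of this analysis to the SAP.
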